5.6.3.7. Procedures for Immune-Mediated Nephritis or Renal Dysfunction

Subjects should be monitored for signs and symptoms that may be related to changes in renal function (eg, routine urinalysis, elevated serum blood urea nitrogen and creatinine, decreased creatinine clearance, electrolyte imbalance, decrease in urine output, proteinuria). Consult with a nephrologist. Subjects should be thoroughly evaluated to rule out any alternative etiology (eg, disease progression, infections). Steroids should be considered in the absence of clear alternative etiology even for low-grade events (Grade 2) in order to prevent potential progression to higher grade event. Recommendations are shown in [Table 16](#).

Table 16: Recommended Approach for Handling Nephritis or Renal Dysfunction

Toxicity Grade	Withhold/Discontinue Epacadostat and Durvalumab	Guidance for Restarting Study Treatment	Supportive Care
Grade 1	No action.	Not applicable.	For Grade 1 elevated creatinine: 
 • Monitor serum creatinine weekly and any accompanying symptom 
 – If creatinine returns to baseline, resume its regular monitoring per study Protocol. – If it worsens, depending on the severity, treat as Grade 2 or Grade 3 or Grade 4. • Consider symptomatic treatment, including hydration, electrolyte replacement, diuretics, etc.
Grade 2	Withhold epacadostat and durvalumab.	Resume study treatment at same dose/schedule when nephritis is controlled. Hold study treatment until resolution to \leq Grade 1 or baseline. 
 • If toxicity worsens, then treat as Grade 3 or Grade 4. • If toxicity improves to \leq Grade 1 or baseline, then resume study treatment after completion of steroid taper. Study treatment can be resumed at the next scheduled dose once event stabilizes to \leq Grade 1 and 5-7 days have passed after completion of steroid taper.	For Grade 2 elevated creatinine: 
 • Consider symptomatic treatment, including hydration, electrolyte replacement, diuretics, etc. • Carefully monitor serum creatinine as clinically warranted. • Consult nephrologist and consider renal biopsy if clinically indicated. • If event is persistent ($>$ 3-5 days) or worsens, promptly start prednisone 1-2 mg/kg per day PO or IV equivalent. • If event is not responsive within 3-5 days or worsens despite prednisone 1-2 mg/kg per day PO or IV equivalent, additional work-up should be considered and prompt treatment with IV methylprednisolone 2-4 mg/kg per day started. • Once improving, gradually taper steroids over \geq 28 days and consider prophylactic antibiotics, antifungals, and anti-PCP treatment (refer to current NCCN Guidelines for treatment of cancer-related infections [Category 2B recommendation]). • When event returns to baseline, resume study treatment and routine serum creatinine monitoring per study Protocol.

Table 16: Recommended Approach for Handling Nephritis or Renal Dysfunction (Continued)

Toxicity Grade	Withhold/Discontinue Epacadostat and Durvalumab	Guidance for Restarting Study Treatment	Supportive Care
Grade 3 or Grade 4	Discontinue epacadostat and durvalumab.	Not applicable.	
 • Carefully monitor serum creatinine on daily basis. • Consult nephrologist and consider renal biopsy if clinically indicated. • Promptly start prednisone 1-2 mg/kg per day PO or IV equivalent. • If event is not responsive within 3-5 days or worsens despite prednisone 1-2 mg/kg per day PO or IV equivalent, additional work-up should be considered, and prompt treatment with IV methylprednisolone 2-4 mg/kg per day started. • Once improving, gradually taper steroids over ≥ 28 days and consider prophylactic antibiotics, antifungals, and anti-PCP treatment (refer to current NCCN Guidelines for treatment of cancer-related infections [Category 2B recommendation]).

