Grade 2	Withhold epacadostat and durvalumab. Note: Permanently discontinue study treatment if upon rechallenge subject develops pneumonitis \geq Grade 2.	Hold treatment until resolution to \leq Grade 1 or baseline. 
 • If toxicity improves to \leq Grade 1 or baseline, then the decision to reinstate study treatment will be based on treating physician's clinical judgment and after completion of steroid taper. • If toxicity worsens, treat as Grade 3 or Grade 4. 	For Grade 2 (mild to moderate new symptoms): 
 • Monitor symptoms daily and consider hospitalization. • Promptly start systemic steroids (eg, prednisone 1-2 mg/kg per day PO or IV equivalent). • Reimaging as clinically indicated. • If no improvement within 3-5 days, additional work-up should be considered, and prompt treatment with IV methylprednisolone 2-4 mg/kg per day should be started. • If still no improvement within 3-5 days despite IV methylprednisone at 2-4 mg/kg per day, promptly start immunosuppressive therapy such as tumor necrosis factor inhibitors (eg, infliximab 5 mg/kg every 2 weeks). Caution: Important to rule out sepsis and refer to infliximab label for general guidance before using infliximab. • Once improving, gradually taper steroids over \geq 28 days and consider prophylactic antibiotics, antifungal or anti-PCP treatment (refer to current NCCN Guidelines for treatment of cancer-related infections [Category 2B recommendation]). • Consider pulmonary and infectious disease consult. • Consider discussing with medical monitor as necessary.

Table 10: Recommended Approach for Handling Noninfectious Pneumonitis (Continued)

Toxicity Grade	Withhold/Discontinue Durvalumab and Epacadostat	Guidance for Restarting Study Treatment	Supportive Care

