Grade 2	Withhold durvalumab and epacadostat.	
Hold treatment until resolution to \leq Grade 1 or baseline.
 
 • If toxicity improves to \leq Grade 1, then study treatment can be resumed after completion of steroid taper. Epacadostat will be reduced by 1 dose level, and durvalumab will resume at the same dose/schedule. • If toxicity worsens, treat as Grade 3 or Grade 4. 	
 • Consider symptomatic treatment, including hydration, electrolyte replacement, dietary changes (eg, American Dietetic Association colitis diet), and loperamide and/or budesonide. • Promptly start prednisone 1-2 mg/kg per day PO or IV equivalent. • If event is not responsive within 3-5 days or worsens despite prednisone 1-2 mg/kg per day PO or IV equivalent, GI consult should be obtained for consideration of further work-up such as imaging and/or colonoscopy to confirm colitis and rule out perforation, and prompt treatment with IV methylprednisolone 2-4 mg/kg per day started. • If still no improvement within 3-5 days despite 2-4 mg/kg IV methylprednisolone, promptly start immunosuppressives such as infliximab at 5 mg/kg once every 2 weeks. 
Caution: Important to rule out bowel perforation and refer to infliximab label for general guidance before using infliximab.
 
 • Consult with medical monitor if no resolution to \leq Grade 1 in 3-4 days. • Once improving, gradually taper steroids over \geq 28 days and consider prophylactic antibiotics, antifungals, and anti-PCP treatment (refer to current NCCN Guidelines for treatment of cancer-related infections [Category 2B recommendation]).

Table 11: Recommended Approach for Handling Enterocolitis (Continued)

Toxicity Grade	Withhold/Discontinue Durvalumab and Epacadostat	Guidance for Restarting Study Treatment	Supportive Care

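### The Grade 2 nephritis row of Table 16 gives conflicting restart conditions, and two of its lines allow re-dosing before a steroid taper is complete

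*Protocol*

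**What the plan says.** Table 16 (Protocol Section 5.6.3.7) withholds both drugs for Grade 2 nephritis or renal dysfunction. It then gives these restart instructions, lettered here for reference:

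- **(a)** Restart cell, opening line: "Resume study treatment at same dose/schedule when nephritis is controlled". The next line says to "Hold study treatment until resolution to" Grade 1 or lower, or baseline.
- **(b)** Restart cell, bullet: on improvement to Grade 1 or lower or baseline, "then resume study treatment after completion of steroid taper".
- **(c)** Restart cell, closing line: restart at the next scheduled dose once the event has stabilised at Grade 1 or lower and "5-7 days have passed after completion of steroid taper".
- **(d)** Supportive Care cell, last bullet: "When event returns to baseline, resume study treatment and routine serum creatinine monitoring per study Protocol".

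The same row brings in steroids. If the event lasts more than 3-5 days or worsens, sites are to "promptly start prednisone 1-2 mg/kg per day PO or IV equivalent" and, once it is improving, to taper over at least 28 days. The text above the table says steroids should be considered even at Grade 2 when there is no clear alternative cause.

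**The concern.** All four lines apply to the same event in the same patient, but they set different conditions. Lines (a) and (d) say nothing about the taper, (b) requires it to be finished, and (c) adds a wait after that. Neither the row nor the rest of Section 5.6.3.7 ranks them, and control is not defined. A steroid-treated patient whose creatinine recovers during the taper may be restarted under (a) or (d) but not under (b) or (c). Two sites could each follow the Protocol to the letter and treat identical patients differently on a safety decision. Durvalumab is given every 14 days (Section 5.1.2), so about 28 / 14 = 2 infusions could fall within a minimum-length taper.

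**Working it through.** The plan states no figure to reproduce. The check sets the lines side by side, works out the timing, and looks for a rule elsewhere that settles the matter.

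**1. The lines compared**

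| Line | Resolution required | Taper completed? | Extra wait |
|---|---|---|---|
| (a) | Controlled (undefined); next line holds to Grade 1 or lower, or baseline | Not mentioned | None |
| (b) | Grade 1 or lower, or baseline | Required | None |
| (c) | Grade 1 or lower | Required | 5-7 days |
| (d) | Baseline | Not mentioned | None |

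Line (a) could be read as a dose instruction only, although it is worded as a timing rule. Even on that reading, (d) conflicts with (b) and (c), and (b) conflicts with (c).

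**2. Timing for a steroid-treated patient**

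Inputs from Table 16: minimum taper 28 days; extra wait 5-7 days. Assumption, because the documents give no value: control or baseline is reached on taper day *t* = 0, 14 or 28.

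Earliest restart, counted from the start of the taper, is day *t* under (a) or (d), day 28 under (b), and day 28 + 5 = 33 to 28 + 7 = 35 under (c).

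Gap between loosest and strictest lines = (28 − *t*) + 5 to 7 days:

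- *t* = 0: 28 + 5 to 7 = 33 to 35 days
- *t* = 14: 14 + 5 to 7 = 19 to 21 days
- *t* = 28: 0 + 5 to 7 = 5 to 7 days

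Gap between (b) and (c), whatever the value of *t*: 5 to 7 days.

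Without steroids there is no taper term, and the lines differ only in the resolution endpoint.

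**3. What the other Grade 2 rows do**

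Tables 10-15, 17-19 and 21 contain 11 other Grade 2 rows (Table 14 has two).

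- Seven tie restart to a completed taper: pneumonitis, enterocolitis, hepatitis, dermatitis, neurotoxicity, endocrinopathy (with an exception for low-dose replacement) and myocarditis. For pneumonitis the decision rests on the treating physician's "clinical judgment and after completion of steroid taper". For enterocolitis, on improvement to Grade 1 or lower, "then study treatment can be resumed after completion of steroid taper".
- Four do not: neuromotor syndromes, lipase or amylase elevation, myositis, and the residual category in Table 21.

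**4. Is there an overriding rule?**

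- Section 5.6.3 requires immediate discussion of any Grade 2 or higher immune-related event with the medical monitor. It sets no restart criterion.
- Sections 5.6.2 and 5.7.1 bring in the medical monitor for interruptions or delays over 4 weeks. Under (b) or (c), a 28-day taper that begins after the hold has started will ordinarily pass that limit. Under (a) or (d), restart can come sooner and avoid the check.
- Section 5.6.3.12 allows restart once the taper has reached 10 mg/day prednisone or less, but it covers events not described in the earlier sections.

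None of these chooses between the four lines.

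**The case against.** The strongest reply is that the row can be read as a whole. On that reading the opening line gives the dose, the hold line defines control, and the bullet adds the taper. The baseline line sits under Supportive Care, directly after the taper bullet, and mainly concerns the return to routine creatinine monitoring. A careful site would apply every line and so follow the strictest. That reading is available, but the text does not require it, and it resolves the 5-7 day difference between (b) and (c) only by defaulting to the stricter line.

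There is also more oversight than the row shows. Sections 5.10.1 and 5.10.2 require medical monitor approval for systemic steroids during treatment, so a patient on a taper is already known to the monitor. This makes an unsupervised early restart less likely. The approval covers the steroid rather than the timing of re-dosing, and a monitor asked about restart would turn to this same row.

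Nor is a completed taper a universal rule in this Protocol. Section 5.6.3.12 accepts a taper to 10 mg/day, and the Grade 2 myositis row prescribes steroids and a taper but sets no taper condition for restart. The endocrinopathy row, counted among the seven, also opens with a line that omits the taper. These points stand: completion is the majority pattern only. The fault here is that one row contradicts itself, whichever policy is preferred.

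Finally, the day-0 case is extreme, because the taper starts only once the event is improving, and the table is headed as recommended guidance. Both points are fair, and they bear on size rather than on whether the conflict exists.

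**Conclusion.** The concern holds. Table 16 gives four restart instructions for one Grade 2 event. Two of them, followed as written, permit re-dosing during a taper that the other two require to be finished. The only gap fixed by the text is the 5-7 days between the two lines that both require completion. The wider gaps of 19-21 and 33-35 days rest on the minimum 28-day taper and on assumed recovery at taper day 14 or 0. The problem is confined to Grade 2 nephritis treated with steroids, medical monitor contact reduces it, and it has no direct effect on the statistical design. It should be corrected because it is a safety instruction that contradicts itself.

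**What to change.** In the Grade 2 restart cell of Table 16, keep the same-dose-and-schedule wording as the dose instruction only, and delete control of nephritis as a timing rule. Make that cell and the last Supportive Care bullet state one condition: Grade 1 or lower or baseline, **and** steroid taper completed if steroids were given. This is already line (b), and it matches seven of the other Grade 2 rows. The clinical team should decide whether the 5-7 day wait after the taper applies to all steroid-treated patients or is removed, and state the result once.

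The cost is a wording change to two cells of one table row, by protocol clarification letter or with the next amendment.

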5.6.3.8. Procedures and Guidelines for Lipase or Amylase Elevations

Subjects should be carefully monitored for signs and symptoms of pancreatitis, including upper abdominal pain, abdominal pain that radiates to the back, abdominal pain that feels worse after eating, fever, rapid pulse, nausea, vomiting, and tenderness when touching the abdomen. If any symptoms occur, dosing should be held, and, if severe, abdominal imaging should be considered and treatment should be permanently discontinued. Recommendations for the management of lipase or amylase elevations are provided in [Table 17](#).

Table 17: Recommended Approach to Handling Lipase or Amylase Elevations

Toxicity Grade	Withhold/Discontinue Epacadostat and Durvalumab	Guidance for Restarting Study Treatment	Supportive Care
Grade 1	No action.	Not applicable.	Not applicable.
Grade 2	Subjects with intolerable or persistent Grade 2 toxicity may hold study treatment per investigator discretion.	If held, study treatment may resume when toxicity resolves to \leq Grade 1.	Not applicable.
Grade 3	
 • If asymptomatic, may continue study treatment with medical monitor approval. • Permanently discontinue study treatment if clinical signs and symptoms of pancreatitis develop (eg, abdominal pain, nausea, vomiting). • If toxicity does not resolve to \leq Grade 1 within 12 weeks of last dose after interruption, study treatment must be permanently discontinued unless approved by the medical monitor. 	If held, study treatment may resume when toxicity resolves to \leq Grade 1.	Not applicable unless symptomatic; then treat with systemic corticosteroids at a dose of 1-2 mg/kg per day prednisone or equivalent.
Grade 4	
 • Withhold epacadostat and durvalumab. • If lipase/amylase elevation is asymptomatic and abdominal imaging suggests no pathology, study treatment may continue with medical monitor approval. • Permanently discontinue if clinical signs and symptoms of pancreatitis develop (eg, abdominal pain, nausea, vomiting). • If toxicity does not resolve to \leq Grade 1 within 12 weeks of last dose after interruption, study treatment must be permanently discontinued unless approved by the medical monitor. 	If held, study treatment may resume when toxicity resolves to \leq Grade 1.	May consider treatment with systemic corticosteroids at a dose of 1-2 mg/kg per day prednisone or equivalent.

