5.7. Withdrawal of Subjects From Study Treatment

5.7.1. Withdrawal Criteria

Subjects **must** be withdrawn from study treatment for the following reasons:

- The subject completes 12 months of study treatment with epacadostat and durvalumab, or had completed 12 months of combination treatment (prior to Amendment 6 [28 JUN 2017]), and has taken epacadostat monotherapy for an additional 12 months (for a total of 24 months of study treatment).
 - Note: A subject may be granted an exception by the medical monitor to continue on epacadostat monotherapy beyond 24 months of overall treatment duration if they are clinically stable or clinically improved. Approvals to remain on epacadostat monotherapy will require continuing review every 3 months.
- In the investigator's medical judgment, further participation would be injurious to the subject's health or well-being.
- The subject becomes pregnant.
- Consent is withdrawn by subject or legal representative (such as legal guardian).
- The subject has experienced an unacceptable toxicity as described in Section 5.6 or a toxicity that does not recover in 4 weeks. Investigators who wish to continue treatment after a treatment delay of 4 weeks should consult with the sponsor's medical monitor for approval.
- Confirmed radiographic progression of disease per modified RECIST v1.1. See Section 7.4 for details on subjects with unconfirmed radiographic progression. An exception to continue on treatment with confirmed radiographic progression may be granted to clinically stable subjects. See Section 7.4 for additional details.
- The study is terminated by the sponsor.
- The study is terminated by the local health authority or IRB or IEC.
- \geq Grade 3 infusion reaction.
- Initiation of alternative anticancer therapy including another investigational agent.

A subject **may** be withdrawn from the study treatment as follows:

- If subject attains a CR (see Section 7.4.3), and the decision is made to discontinue durvalumab.
- If, during the course of the study, a subject is found not to have met eligibility criteria, the medical monitor, in collaboration with the investigator, will determine whether the subject should be withdrawn from study treatment. See Section 11.3, Protocol Adherence.
- If a subject is noncompliant with study procedures or study drug administration in the opinion of the investigator, the sponsor should be consulted for instruction on handling the subject.

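### Section 5.6.3.8 and Table 17 conflict on whether a subject with Grade 3-4 lipase/amylase elevation and non-severe pancreatitis symptoms may resume treatment, and Table 17's 12-week limit is not squared with the 4-week rules in 5.6.2 and 5.7.1

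*Protocol*

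**What the plan says.** The narrative of Protocol Section 5.6.3.8 lists pancreatitis symptoms, among them abdominal pain, nausea and vomiting, and then gives a two-step rule: "If any symptoms occur, dosing should be held, and, if severe, abdominal imaging should be considered and treatment should be permanently discontinued". This rule turns on symptoms alone. It carries no enzyme-grade condition, and it does not define severe.

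Table 17, which follows, is organised by toxicity grade:

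- Grade 1: no action.
- Grade 2: "Subjects with intolerable or persistent Grade 2 toxicity may hold study treatment per investigator discretion". Pancreatitis symptoms are not mentioned.
- Grade 3: "Permanently discontinue study treatment if clinical signs and symptoms of pancreatitis develop (eg, abdominal pain, nausea, vomiting".
- Grade 4: "Permanently discontinue if clinical signs and symptoms of pancreatitis develop (eg, abdominal pain, nausea, vomiting".
- Grades 3 and 4, if the toxicity has not come down to Grade 1 or less: "within 12 weeks of last dose after interruption, study treatment must be permanently discontinued unless approved by the medical monitor".

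Section 5.7.1 includes this in its list of reasons for which a subject must be withdrawn from treatment: "The subject has experienced an unacceptable toxicity as described in Section 5.6 or a toxicity that does not recover in 4 weeks". It then directs investigators who want to go on after a 4-week delay to seek the medical monitor's approval. Section 5.6.2 states, as a general rule, that treatment ends for toxicities not down to Grade 1 or less within 4 weeks of onset. It refers exceptions to the medical monitor, and it requires a discussion with the monitor before treatment resumes after any interruption longer than 4 weeks.

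**The concern.** Two rules in one section act on the same event but use different triggers. The narrative uses symptom severity; the table uses laboratory grade plus the presence of symptoms. Neither refers to the other as the governing rule, so whether a subject may return to treatment can depend on which lines the site reads. The time limit raises the same problem across sections.

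Pancreatitis is among the risks that Protocol Section 1.3.2.2.1 names for durvalumab monotherapy, and lipase and amylase are in the required chemistry panel (Table 26), so elevations will be picked up routinely. At stake is consistent handling of subjects after a possible pancreatitis signal. There is also a reporting consequence: SAP Section 8.2.2 tabulates adverse events leading to interruption and to permanent discontinuation, and those counts would mix different site readings.

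**Working it through.** No sample size, power or error rate is involved, and the plan gives no figure to reproduce. The check sets the passages side by side.

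**Symptoms.** Inputs: the Section 5.6.3.8 narrative and the four grade rows of Table 17. Crossing four grades with two symptom levels gives 4 × 2 = 8 combinations.

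| Enzyme grade | Symptoms | Narrative | Table 17 | Result |
|---|---|---|---|---|
| 1 | non-severe | hold | no action | differ |
| 1 | severe | permanent stop | no action | differ |
| 2 | non-severe | hold | optional hold, if intolerable or persistent | differ |
| 2 | severe | permanent stop | optional hold, if intolerable or persistent | differ |
| 3 | non-severe | hold | permanent stop | conflict |
| 3 | severe | permanent stop | permanent stop | agree |
| 4 | non-severe | hold | permanent stop | conflict |
| 4 | severe | permanent stop | permanent stop | agree |

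Six combinations differ and two agree. The two Grade 3-4 non-severe rows are direct conflicts, because both passages address symptoms and prescribe different consequences. A subject held under the narrative could use the table's restart column once the toxicity is back to Grade 1 or less. The table's own symptom line closes that route. In the four Grade 1-2 rows the table is silent on pancreatitis symptoms, so the disagreement is one of unstated precedence.

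**Time limit.** Inputs: 12 weeks from last dose (Table 17, Grades 3 and 4); 4 weeks from onset (5.6.2); 4 weeks with no start point given (5.7.1); 14-day cycles (5.4).

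Let d be the number of weeks from onset to last dose. The documents do not give d, so it is an assumption here. Measured from onset, Table 17's limit falls at 12 + d weeks and that of 5.6.2 at 4 weeks. The gap is (12 + d) − 4 = 8 + d weeks.

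- d = 0 (dosing stops at onset): 8 weeks, or 8/2 = 4 cycles.
- d = 2 (dosing continues two weeks after onset): 10 weeks, or 5 cycles.
- d = −2 (last dose two weeks before onset): 6 weeks, or 3 cycles.

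For 5.7.1 the gap cannot be computed without assuming a start. If its clock also starts at onset, the same figures apply.

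**Example.** An asymptomatic subject at Grade 3 is held at onset and returns to Grade 1 at week 6. Table 17 lets treatment resume, because its limit has not been reached. Under 5.7.1, if its 4 weeks run from onset, the subject should have been withdrawn at week 4 unless the medical monitor approved continuing. Section 5.6.2 would require a discussion with the monitor before restart.

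**The case against.** The best defence has four parts.

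First, a reader might infer that the two passages give opposite instructions. They do not. For a symptomatic Grade 3 or 4 subject both stop dosing at once; Table 17 contemplates continuing only for asymptomatic elevations. The disagreement is confined to whether the subject may come back. That limit stands, but the disagreement remains.

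Second, the Grade 1-2 rows can be read together with the narrative: a symptom rule that applies at any grade, laid over a laboratory-grade table. The narrative also says should, so calling its hold mandatory overstates it. This reading is reasonable, but the protocol does not state it, so what is left is a clarity gap.

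Third, severe might be taken to mean toxicity of Grade 3 or higher, which would shrink the Grade 3-4 conflict. The sentence attaches the word to symptoms and leaves it undefined, so that reading has to be supplied by the site.

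Fourth, event-specific limits sit beside the general rule elsewhere (14 days in Table 12, 30 days in Tables 14 and 19), Section 5.6.2 speaks only in general terms, and all three places allow medical monitor exceptions. A site could obey them all by obtaining approval beyond 4 weeks and again at 12. This softens the mismatch considerably. It does not remove it, because 5.7.1 is a list of compulsory reasons with no lipase/amylase exception, and Table 17 does not mention approval at 4 weeks. Table 13 shows that a table can do so: Grade 3 dermatitis unresolved at 4 weeks needs the monitor's approval to restart.

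Section 5.6.3 also asks that immune-related events of Grade 2 or higher be discussed immediately with the medical monitor. That should reduce divergence between sites, but it does not tell the monitor which passage governs.

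**Conclusion.** The point holds in a bounded form. For Grade 3 or 4 elevations with non-severe pancreatitis symptoms, the narrative and Table 17 disagree on whether treatment may resume. For Grades 1 and 2 with symptoms, they differ and no precedence is stated. The 12-week and 4-week limits are not reconciled: they start at different or unstated points, and they bring in the medical monitor at different times. This rests on reading severe as a description of symptoms, which is how the sentence is built. It takes no view on which clinical rule is right.

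Three stronger inferences are not supported:

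- That the limits differ threefold. The ratio 12/4 compares clocks with different starting points.
- That the nausea and vomiting rates in Sections 1.3.2.2.1 and 1.4 size the affected group. Those are overall rates, on durvalumab alone or on epacadostat with ipilimumab. The conflict needs pancreatitis symptoms together with an enzyme elevation, and the documents give no rate for that joint event.
- That discontinuation rates form the Phase 2 safety endpoint. Section 4.2.2 defines that endpoint by the frequency, duration and severity of adverse events, with examinations, vital signs, ECGs and laboratory tests. Discontinuation for an adverse event is one of the SAP's planned summaries.

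The number of subjects affected therefore cannot be stated. The inconsistency is worth correcting because it bears on stopping treatment and is cheap to remove.

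**What to change.** Reconcile the Section 5.6.3.8 narrative, every row of Table 17, and the 4-week provisions of Sections 5.6.2 and 5.7.1. For each grade, state once:

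- what follows when pancreatitis symptoms occur;
- whether symptom severity changes that action and, if so, how severe is defined;
- which time limit applies and the day it counts from;
- when medical monitor approval is needed;
- which passage governs if two apply.

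If a limit specific to lipase and amylase is intended, name it as an exception in 5.7.1. The same edit can correct the overview in Section 5.6.3, which omits lipase/amylase and gives 5.6.3.8 as the location of the ocular guidance, now in 5.6.3.9. The sponsor must decide the clinical content. The cost is protocol wording only, with no new assessments.
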